8.2 Adverse Reactions

An AE is considered related to study drug (adverse reaction) if there is evidence to suggest a causal relationship between the treatment and the AE.

8.3 Suspected Adverse Reactions

“Suspected adverse reactions” means any AE for which there is a reasonable possibility that the drug caused the AE. “Reasonable possibility” means there is evidence to suggest a causal relationship between the drug and the AE. A “suspected adverse reaction” implies a lesser degree of certainty about causality than “adverse reaction” which means any AE caused by a drug.

An AE is considered to be a suspected adverse reaction if:

- The AE is a single occurrence of an uncommon AE that is known to be strongly associated with drug exposure (eg, angioedema, hepatic injury, Stevens-Johnson Syndrome).
- The AE occurs 1 or more times and is not commonly associated with drug exposure, but is otherwise uncommon in the population exposed to the drug (eg, tendon rupture).
- The AE is part of an aggregate analysis of specific AEs observed in a clinical trial (such as known consequences of the underlying disease or condition under investigation or other events that commonly occur in the study population independent of drug therapy) that indicates those AEs occur more frequently in the drug treatment group than in a concurrent or historical control group.

Suspected adverse reactions are the subset of all AEs for which there is a reasonable possibility that the drug caused the event. Inherent in this definition and in the requirement to report them, is the need for the Sponsor to evaluate the available evidence and make a judgment about the likelihood that the drug actually caused the AE.

8.4 Unexpected Adverse Reactions or Adverse Events

An AE or suspected adverse reaction is considered “unexpected” if it is not listed in the IB or is not listed at the specificity or severity that has been observed. “Unexpected,” as used in this definition, also refers to AEs or suspected adverse reactions that are mentioned in the IB as occurring with a class of drugs or as anticipated from the pharmacological properties of the drug, but are not specifically mentioned as occurring with the particular drug under investigation.

The suspected adverse reactions listed in the IB (ie, “expected”) are those observed with the investigational drug and for which a causal relationship between the event and the drug is suspected or confirmed. Thus, AEs that would be anticipated to occur as part of the disease process are considered *unexpected* for the purposes of reporting because they would not be listed in the IB. Additionally, AEs that are listed in the IB as occurring with the same class of drugs, or as

anticipated from the pharmacological properties of the drug, even though they have not been observed with the drug under investigation, will be considered *unexpected* until they have been observed with the drug under investigation.

8.5 Serious Adverse Events

An AE or suspected adverse reaction is considered “serious” if at any dosage, in the view of either the investigator or Sponsor, it meets one or more of the following criteria:

- is fatal
- is life-threatening
- results in inpatient hospitalization or prolongation of existing hospitalization
- results in a persistent or significant incapacity or substantial disruption of the ability to conduct normal life functions
- is a congenital anomaly/birth defect

Other important medical events that may not be immediately life-threatening or result in death or hospitalization, based upon appropriate medical judgment, are considered SAEs if they are thought to jeopardize the subject and/or require medical or surgical intervention to prevent one of the outcomes defining an SAE. Since SAEs are critically important for the identification of significant safety problems, it is important to take into account both the investigator’s and the Sponsor’s assessment. If either the Sponsor or investigator believes that the event is serious, the event must be considered serious and evaluated by the Sponsor for expedited reporting.

All SAEs must be reported to the Sponsor or their designee within 24 hours after the investigator becomes aware of the event, along with a determination as to whether it is associated with the study drug, device, or procedure.

8.5.1 Life-Threatening Adverse Events

An AE or suspected adverse reaction is considered “life-threatening” if, in the view of either the investigator or Sponsor, its occurrence places the subject at immediate risk of death. It does not include an AE or suspected adverse reaction that, had it occurred in a more severe form, might have caused death. As with the definition of serious, the determination of whether an AE is life-threatening can be based on the opinion of either the investigator or Sponsor. Thus, if either believes that it meets the definition of life-threatening, it must be considered life-threatening for reporting purposes.

8.5.2 Serious Adverse Event Reporting

All SAEs must be reported within 24 hours to:

PPD

Safety Email: [contact]

Safety [contact]

Note: If the contact information above changes during the course of the study, written notification will be provided by the Sponsor or their designee to the investigator, and a protocol amendment will not be required.

It is imperative that PPD be informed within 24 hours after the investigator becomes aware of a SAE so that reporting to the Regulatory Agencies can be met within the required time frame (7 or 15 calendar days).

Because of the need to report to health authorities all SAEs in a timely manner, it is vitally important that an investigator report any AEs that would be considered serious within 24 hours, even if the investigator does not consider the AE to be clinically significant or drug-related.

Should the investigator become aware of an SAE (regardless of relationship to study drug) that occurs within 30 days after stopping the study drug, the SAE must be reported in accordance with the procedures specified in this protocol. There is no time limit on the collection of SAEs that are considered related to study drug.

All SAEs that are not resolved by the end of the study, or that were not resolved upon discontinuation of the subject's participation in the study, are to be followed until either: the AE resolves, the AE stabilizes, the AE returns to baseline values (if a baseline value is available), or it is shown that the AE is not attributable to the study drug or study conduct.

Medical and scientific judgment is to be exercised in deciding whether expedited reporting is appropriate in other situations, such as for important medical events that were not immediately life-threatening or did not result in death or hospitalization but are jeopardizing the subject or require intervention to prevent one of the outcomes listed above.

8.6 Non-Serious Adverse Event Reporting

Non-SAEs will be recorded in the clinical data base in a timely manner to permit review by the Sponsor.

8.7 Pregnancy

Following administration of study drug, pregnancy cases in any female subject will be reported if known until the subject completes or withdraws from the study. The pregnancy will be reported immediately by phone and by faxing/emailing a completed Pregnancy Report to the Sponsor or their designee within 24 hours of knowledge of the event. The pregnancy will not be processed as an SAE; however, the investigator will follow the subject until completion of the pregnancy and must assess the outcome in the shortest possible time but not more than 30 days after completion of the pregnancy. The investigator should notify the Sponsor or their designee of the pregnancy outcome by submitting a follow-up Pregnancy Report. If the outcome of the pregnancy meets the criteria for immediate classification of an SAE (eg, spontaneous or therapeutic abortion [any congenital anomaly detected in an aborted fetus is to be documented], stillbirth, neonatal death, or congenital anomaly), the investigator will report the event by phone and by faxing/emailing a completed SAE form to the Sponsor or designee within 24 hours of knowledge of the event. Pregnancy in the partners of research subjects does not need to be reported.

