- ^a All visits up to Visit 6 (Week 24) should be scheduled based on the date of the Day 1 visit. If necessary, visits may be performed within the time window shown; however, subsequent visits should be scheduled based on the date of the Day 1 visit.
- ^b The assignment of a kit number for the demonstrator model EDS is not performed by IWRS, rather, the study staff will dispense a demonstrator model EDS kit and record the kit number in the drug dispensing log. This practice EDS is only used at the site at Visit 1 (Screening) and is not to be sent home with the subject.
- ^c Women of child-bearing potential only; urine pregnancy tests will be performed at each visit, not including subject contacts. Subjects continuing treatment past Week 24/Visit 6 will need an additional pregnancy test completed upon returning to site.
- ^d Nasoendoscopy will be performed using a rigid or flexible endoscope. The examiner must be able to visualize the middle meatus with the scope. Decongestants and/or local anesthetics may be used for the nasoendoscopic procedure.
- ^e The CT scan should be performed after diary eligibility is confirmed and prior to Day 21 of the screening run-in period.
- ^f For the Week 24 study visit, the CT examination should be performed prior to the on-site visit.
- ^g Demonstrator model EDS kit (see footnote b) and single-blind placebo dispensation only.
- ^h At Visit 1 (Screening), the IWRS will be contacted to obtain the subject ID number, the identifier for the single-blind kit to be dispensed and to track enrollment. IWRS will be contacted at Visit 2 to randomly assign subjects to treatment. At Visit 2 through – Visit 5, IWRS will be used to assign the study

drug kit(s) to be dispensed. If a subject cannot complete the EOS CT scan at Visit 6 (Week 24), study staff should not complete Visit 6 in IWRS. Subjects should continue study treatment until an EOS CT scan can be completed. Study staff will dispense additional study medication via the “Unscheduled Visit” functionality in IWRS. IWRS will be contacted for each ‘Unscheduled Visit,’ at which time one treatment kit will be dispensed.

- i The period of observation for collection of AEs extends from the time the subject gives informed consent until completion of the double-blind treatment period or an early termination visit. Serious adverse events will be reported through 30 days after the last dose of study drug administration.

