For the purposes of this study, the period of observation for collection of AEs extends from the time the subject gives informed consent until completion of the end-of-study visit or an early termination visit. SAEs will be reported through 30 days after the last dose of study drug administration.

The maximum severity (intensity) of the AE will be categorized by the investigator as shown in [Table 5](#).

Table 5: Adverse Event Severity

Code	Descriptor	Definition
1	Mild	The subject is aware of the symptom, but easily tolerates it
2	Moderate	The subject has discomfort enough to cause interference with usual activity.
3	Severe	The subject is incapacitated to work or perform the usual activities

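### Section 8.7 sets no duty to report or follow an on-drug conception first recognised after the subject leaves the study, although SAEs are collected to 30 days after the last dose

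*Protocol*

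**What the plan says.** Protocol section 8.7 governs pregnancies after study drug has been given. Its window closes at study exit: "pregnancy cases in any female subject will be reported if known until the subject completes or withdraws from the study". A pregnancy reported inside that window is followed to its end, even if the study is over by then. The section keeps the pregnancy apart from SAE handling ("The pregnancy will not be processed as an SAE"), but it sends certain outcomes, among them abortion, stillbirth, neonatal death and congenital anomaly, to the SAE route ("If the outcome of the pregnancy meets the criteria for immediate classification of an SAE").

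The SAE window is longer. Section 8.1 states that "SAEs will be reported through 30 days after the last dose of study drug administration", and footnote i of the Schedule of Study Procedures and Evaluations repeats it: "Serious adverse events will be reported through 30 days after the last dose of study drug administration". Section 8.5.2 applies the 30 days whatever the causal assessment ("Should the investigator become aware of an SAE (regardless of relationship to study drug) that occurs within 30 days after stopping the study drug") and adds: "There is no time limit on the collection of SAEs that are considered related to study drug".

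On testing, footnote c of the Schedule and Table 4 place urine tests at on-site visits only, so none is done at the Week 16 and Week 20 contacts. The last is at Week 24/ET, with one more on return to site for subjects whose treatment is extended. Section 2.5 describes participation of about 26 weeks, made up of screening, run-in and the 24-week double-blind phase. No visit, contact or test is listed after that.

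**The concern.** For a subject who completes on drug, study exit and last dose fall at about the same time, so the pregnancy window gives little or no cover after dosing ends. A conception in the last days or weeks on drug can be negative at the final test and come to light only later. A site that followed section 8.7 exactly would then have nothing it must report and no pregnancy it must follow.

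At stake is the completeness of the record of drug-exposed pregnancies. The protocol otherwise takes pregnancy seriously: contraception or abstinence is required of women of child-bearing potential (section 4.1), treatment must stop on pregnancy (section 4.3), tests are done at every on-site visit, and reports are due within 24 hours. An exit-day cut-off fits poorly with those provisions. Efficacy endpoints, estimands, power and error control are not touched.

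**Working it through.** The plan gives no figure on this point to reproduce. The check compares the windows and then does simple day arithmetic.

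**Windows, for a subject who completes on drug at Week 24**

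| Event | Reporting ends | Days after last dose |
|---|---|---|
| Pregnancy (8.7) | study completion or withdrawal | about 0 |
| SAE, any cause (8.1, 8.5.2, Schedule footnote i) | 30 days after last dose | 30 |
| SAE considered related (8.5.2) | no limit | no limit |

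Because 8.7 takes the pregnancy out of SAE processing, the second and third rows do not cover an uncomplicated pregnancy.

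**Inputs for the size**

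- Treatment period: 24 weeks × 7 = 168 days (protocol).
- Final test taken at about the last dose (Schedule, Week 24/ET).
- Lag L from conception to a positive urine test: not in the documents. Assumed 10 to 21 days, with 14 as a middle value and 7 to 28 as a wider range.

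**Share of treatment days on which a conception would be missed at the final test = L / 168**

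- L = 7: 7/168 = 4.2%
- L = 10: 10/168 = 6.0%
- L = 14: 14/168 = 8.3%
- L = 21: 21/168 = 12.5%
- L = 28: 28/168 = 16.7%

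The gap exists for any L above zero; only its size depends on the assumption. Throughout 7 to 28 days, a conception on the day of the last dose would become detectable within 30 days, so the protocol's own SAE window is long enough to contain these cases.

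**Illustrative absolute number.** The documents give neither the number of women of child-bearing potential nor a pregnancy rate. Assume 50 to 150 such women and 2% to 8% pregnancies per year, and let all of them leave the study at the last dose:

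- low: 50 × 0.02 × 10/365 = 0.03
- high: 150 × 0.08 × 21/365 = 0.69

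That is fewer than one expected case in the whole trial. With 1:1:1 allocation, about two-thirds of these would be on active drug.

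**The case against.** The strongest reply is that this is a design choice and not an error. Section 8.7 separates pregnancy reports from SAE reports, nothing promises them the same window, and section 1 describes low systemic absorption of fluticasone propionate. That is fair: the sections do not contradict each other, and a shorter window could be deliberate. But no reason for it is given, and the effect on late conceptions remains.

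A reader might go further and infer that a late on-drug conception is never reported or followed. The documents do not support that. SAE outcomes keep their route under 8.5.2, and 8.7 sets a minimum duty without barring later reports. What stands is that the SAE route is only a partial substitute. A congenital anomaly found at birth would normally fall well outside 30 days, would then be collected only if considered related, and would depend on the investigator hearing of it without any follow-up duty. A normal outcome would not be captured at all.

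A reader might also infer that early leavers are worse affected, since for an exit at Week 8 the share becomes 10/56 = 17.9% to 21/56 = 37.5%. That is a denominator effect: the undetectable period is the same 10 to 21 days for everyone. It also applies only to those who leave drug and study together. Section 4.3 strongly encourages subjects who stop treatment to stay in the study, where they remain inside the pregnancy window.

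Finally, the consent pages were removed and the pregnancy report form is a separate document, so whether subjects are already told to notify the site of a later pregnancy cannot be judged.

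**Conclusion.** The point holds in a limited form. Section 8.7 leaves an on-drug conception first recognised after study completion or withdrawal with no stated duty to report it or to follow it to outcome. It concerns subjects who leave the study at or soon after the last dose.

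The existence of the gap follows from the text alone. Its size, conceptions in about 6% to 13% of treatment days, rests on the assumed 10 to 21 day lag and on the final test coinciding with the last dose. It is a share of days, not of subjects or pregnancies. This is a minor safety-reporting improvement.

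**What to change.** In section 8.7, replace the end of the window with wording such as: *Pregnancies in female subjects that the site learns of from the first dose of study drug until study completion or withdrawal, or until 30 days after the last dose, whichever is later, will be reported and followed to outcome.* Check the result against sections 8.1 and 8.5.2 and Schedule footnote i, and add an instruction that subjects are asked at the final visit to tell the site of a pregnancy recognised in that period.

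The cost is one sentence and a site instruction, with no extra visit or test. If it is made as a protocol amendment, section 13.2.1 requires prior IRB/EC approval. SAP section 4.3 reports that the interim analysis, planned for when at least half the subjects had reached Week 24/ET, has taken place, so a change would reach only subjects still to exit. An occasional additional pregnancy would have to be followed, including some conceived after the last dose; recording the estimated conception date against the last dose would keep those apart. Capture would still rely on self-report.

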9 STATISTICAL ANALYSIS

A detailed Statistical Analysis Plan (SAP) will be prepared after the protocol is approved. This document will provide further details regarding the definition of analysis variables and analysis methodology to address all study objectives. Statistical analysis principles to address all study objectives are provided below.

9.1 Sample Size Determination

Sample size assumptions were originally generated based on previous Phase 3 studies of OPN-375 in subjects with nasal polyposis and data from a study evaluating the change in maxillary and ethmoid opacification in CRS patients treated with an intramuscular dose of triamcinolone (Pallanch 2013). Updated standard deviation estimates for both co-primary endpoints in this amendment are based on a blinded interim analysis of Protocol OPN-FLU-CS-3205. Based on the results for changes from baseline in morning symptoms among subjects with nasal polyps in the previous studies conducted with OPN-375, a sample of 70 subjects per group (210 total subjects) is sufficient to detect a 0.9 scale difference in 7-day average CSNS (AM instantaneous) between treatments (OPN-375 vs placebo) using a 2-sided test at the 5% significance level with 88% power, and assuming a standard deviation (SD) of 1.7. This sample size is also adequate to detect a 9% difference between treatments in average percent opacification (APOV) using a 2-sided test at the 5% significance level with 88% power, and assuming a SD of 17%. The sample size was estimated for the co-primary efficacy endpoints using Power Analysis and Sample Size Software (PASS 15) (NCSS, 2017).

9.2 Analysis Sets

9.2.1 Intent-to-treat Analysis Set

The intent-to-treat (ITT) analysis set will include all subjects who are randomized regardless of whether they received double-blind treatment.

9.2.2 Safety Analysis Set

The safety analysis set will include all randomized subjects who receive at least one dose of randomized study drug. The treatment group assignment in this population will be defined by the treatment actually received. The safety population will be used for the analysis of safety.

9.2.3 Full Analysis Set (FAS)

The FAS will include all subjects in the ITT set who receive at least one dose of randomized study drug during the double-blinded treatment phase, and have at least one baseline efficacy measure for APOV endpoint, and also have a baseline value and at least one post-baseline value (7-day average AM instantaneous CSNS score) for the CSNS endpoint. Subjects will be included in the treatment group to which they were randomized.

The FAS population will be the primary study population for all efficacy analyses in this study.

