4.3 Withdrawal and Removal of Subjects

Subjects will be informed that they are free to withdraw from study treatment and/or the study at any time at their own request without prejudice to their future medical care, or that they may be withdrawn at any time at the discretion of the investigator or Sponsor for safety, nonadherence to protocol requirements, or administrative reasons (eg, termination of study by Sponsor). Subjects wishing to withdraw from study treatment will be strongly encouraged to continue in the study and have all scheduled study procedures performed.

A subject must be withdrawn from treatment for the following reasons:

- subject becomes pregnant
- A subject's study treatment will be discontinued if the investigator or Sponsor considers it in the subject's best interest to stop treatment, (eg, for safety or significant tolerability reasons such as an AE). Subjects who have one of the following AEs must be withdrawn from study treatment.
- IOP of >21 mm Hg
- nasal septal perforation
- new onset or worsening of cataract

A subject may also be withdrawn from study treatment for the following reasons:

- lack of efficacy
- protocol violation

A subject may be withdrawn from the study for the following reasons:

- withdrawal of consent
- adverse event
- protocol violation that makes it unsafe for the subject to continue in the study
- termination of the study
- lost to follow up
- public health measure
- other

If a subject withdraws from the study after starting study treatment, appropriate follow-up must be conducted wherever possible.

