6.3 Visits 3, 4, and 5 (Weeks 4, 8, and 12)

During the 24-week double-blind treatment phase, subjects will return to the study site at Weeks 4, 8 and 12 to have efficacy and safety assessments performed.

At all visits during the double-blind treatment phase, treatment compliance will be monitored as described in [Section 5.7](#). Subjects will be given a double-blind- study drug kit (containing 2 devices) assigned through the IWRS at Visit 3/Week 4 and Visit 4/Week 8. Subjects will receive 3 kits at Visit 5/Week 12. Subjects will be instructed to bring the study drug kits with them to each visit.

Subjects will be required to keep a daily diary of nasal symptoms through Week 12. The diary will be completed immediately before the morning and evening doses and will include recording of both instantaneous and reflective scores for nasal symptoms (see [Section 7.2](#)). Subjects will also be instructed that the use of rescue medication for CRS symptoms is not allowed until after the Week 4 visit; starting at the Week 4 visit, they will be instructed to record use of the approved rescue medication in the electronic diary. Subjects will be instructed to bring the diary with them to all study visits.

The site staff will continue to monitor electronic diary transmission reports throughout the first 12 weeks of double-blind treatment to ensure that subjects are recording both morning and evening

nasal symptoms and rescue medication use and that the data are being transmitted to the data base. Site staff should follow-up with subjects as necessary to counsel them on completion of the electronic diaries.

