6.5 Visit 6 (Week 24 End-of-Double-Blind/Early Termination)

Subjects who complete the 24-week double-blind treatment phase, and those who prematurely withdraw from the study for any other reason during this phase should return to the study site and have the end-of-study/ET from study visit performed, including a CT scan. If a subject could not complete EOS CT scan at the Week 24 visit, subject should have all other scheduled procedures performed and continue on study treatment until an EOS CT scan can be completed. Additional treatment kits can be dispensed via the 'Unscheduled Visit' functionality and the Visit 6 contact should not be completed in IWRS. If subject continues treatment, study staff will complete subject contacts approximately every 4 weeks to assess safety until subject can complete the EOS CT scan. When EOS CT scan has been completed and subject returns to study site, study staff will perform an additional SNOT-22, urine pregnancy test (women of child-bearing potential only), and contact IWRS to complete Visit 6.

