9.3 Primary Estimand, Intercurrent Events, and Estimation

Primary Objective and Population: The primary objective is to compare the efficacy of intranasal administration of twice-daily doses of 186 and 372 µg of OPN-375 (fluticasone propionate) with placebo in subjects with documented CRS without nasal polyps.

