9.3.4 Estimator and Estimation Method – Primary Analysis

Estimator and estimation method (CSNS): For the co-primary endpoint CSNS, the estimator is the mean difference between treatments (active versus placebo) in change from baseline to the end of Week 4 in the 7-day average total CSNS (instantaneous AM). Estimation is based on a mixed model for repeated measures (MMRM) where changes from baseline to Weeks 2, 4 in the 7-day average total CSNS (instantaneous AM), respectively, are the repeated measures. The MMRM model will employ Restricted Maximum Likelihood (REML) for parameter estimation and the Kenward-Roger method for calculating the denominator degrees of freedom. An unstructured covariance matrix will be used to estimate within-subject error. For the treatment policy estimand, (reference [Section 9.3.3](#), criteria 3c), missing data due to study discontinuation will be estimated within the MMRM model under the assumption that the missing data are missing at random (MAR) and that early discontinuation from the study (prior to Week 4) is unlikely to reflect a treatment effect.

The MMRM model will include categorical effects for previous sinus surgery (Y,N), treatment (OPN-375 186 µg, OPN-375 372 µg, placebo), week (2, 4) treatment-by-week interaction, and the continuous covariate baseline 7-day average total CSNS (instantaneous AM) with baseline-by-week interaction.

Estimator and estimation method (APOV): For the co-primary endpoint APOV, the estimator is the mean difference between treatments (active versus placebo) in the change from baseline to Week 24/ET APOV. Estimation is based on an ANCOVA model including categorical effects for previous sinus surgery (Y,N), treatment (OPN-375 186 µg, OPN-375 372 µg, placebo), and baseline APOV.

For the treatment policy estimand, (reference [Section 9.3.3](#), criteria 3,c), missing data due to study discontinuation will be imputed with a pattern mixture model (PMM) multiple imputation (MI) using the Jump-to-Control (J2C) method. The PMM assumes that the missing data at Week 24/ET on the control arm (placebo) is MAR, and the missing data on the active treatment arms have the profile of the control arm at Week 24/ET.

Multiple imputation using a PMM with J2C method will be conducted using the sequential modeling method as described in ([O’Kelly et al, 2014](#)). Further detail on the MI implementation, and statistical analysis and inference is provided in the SAP.

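### The Full Analysis Set requires a post-baseline diary average, so dosed subjects without one drop out of the CT-based APOV co-primary and time to first exacerbation, neither of which uses the diary

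*Protocol*

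**What the plan says.** Protocol 9.2.3 sets joint conditions for FAS entry: randomisation, at least one double-blind dose, a baseline APOV, and for the diary endpoint the subject must "also have a baseline value and at least one post-baseline value (7-day average AM instantaneous CSNS score) for the CSNS endpoint". There is no exception by endpoint: "The FAS population will be the primary study population for all efficacy analyses in this study". The SAP does not redefine the set, and its Introduction declares no deviation from Amendment 4.0.

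Other parts of the protocol treat APOV differently:

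- The population in 9.3 carries no diary condition. The comparison is "with placebo in subjects with documented CRS without nasal polyps".
- Section 9.3.3 follows a treatment policy strategy after treatment discontinuation: an available Week 24/ET CT is used unless a steroid or surgery event has occurred.
- For APOV, 9.3.4 states that "missing data due to study discontinuation will be imputed with a pattern mixture model (PMM) multiple imputation (MI) using the Jump-to-Control (J2C) method".
- For CSNS, 9.3.4 assumes missing at random and that "early discontinuation from the study (prior to Week 4) is unlikely to reflect a treatment effect". It does not say this for APOV.
- Section 6.5 says that subjects who withdraw early "should return to the study site and have the end-of-study/ET from study visit performed, including a CT scan".
- Section 4.3 says: "Subjects wishing to withdraw from study treatment will be strongly encouraged to continue in the study and have all scheduled study procedures performed".
- Section 6.3 sets the diary period: "Subjects will be required to keep a daily diary of nasal symptoms through Week 12".

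**The concern.** Membership of the analysis set for one co-primary endpoint depends on a post-randomisation variable that the endpoint does not use. APOV is the opacified volume of four sinuses on CT (9.3.1). An exacerbation is defined in 7.2 by symptom worsening, seeking care and escalation of treatment, and is assessed to Week 24, twelve weeks after the diary ends.

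Two kinds of subject are affected. One has a Week 24/ET CT but no qualifying diary average; the observed outcome is set aside, although 6.5 and 4.3 try to obtain it. The other has neither. Section 9.3.4 would give that subject an imputed value with the control-arm profile, but the subject is outside the FAS and is deleted instead. For APOV the FAS asks only for a baseline CT, so the plan clearly intends to keep and impute subjects without a later one. The diary clause defeats that intention for a subgroup that may include the earliest leavers.

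**Working it through.** **Inputs.** Protocol 9.1 gives 70 per group, an APOV difference of 9 points, SD 17, two-sided 5% and 88% power. The share of subjects without a post-baseline diary average is not given, so I assume w = 1%, 3% or 5% of the active arm (0.7, 2.1 or 3.5 of 70), all without a CT. That is an upper case, because 6.5 asks early withdrawers for a CT.

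**Plan's own figure.** SE of the difference = 17 × √(2/70) = 2.87. Power is 87.9% by the normal approximation and 87.5% by the two-sample t test, so the stated 88% reproduces.

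**Effect of deletion in place of jump-to-control.** Imputed active subjects take the placebo profile, so the expected difference is 9 × (1 − w). Under exclusion it stays at 9. The shift is 9w.

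| w | With jump-to-control | With exclusion | Shift (points) | Shift / SE |
|---|---|---|---|---|
| 1% | 8.91 | 9.0 | 0.09 | 0.03 |
| 3% | 8.73 | 9.0 | 0.27 | 0.09 |
| 5% | 8.55 | 9.0 | 0.45 | 0.16 |

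Each such active subject is worth 9/70 = 0.13 points, or 0.04 SE. A placebo subject excluded without a CT causes no expected shift, because placebo data are assumed missing at random.

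**Subjects with an observed CT.** The direction is open. If a scan lay 1-2 SD from its arm mean (17-34 points, an assumption), leaving it out would move that mean by about 17/70 = 0.24 to 34/70 = 0.49 points, either way.

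**Power** (two-sample t, SD 17, imputed values counted as full information, which is an approximation):

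| w | Jump-to-control, 70 v 70 | Exclusion, active arm only | Exclusion, both arms |
|---|---|---|---|
| 1% | 86.8% | 87.3% | 87.2% |
| 3% | 85.5% | 87.0% | 86.5% |
| 5% | 84.0% | 86.6% | 85.8% |

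**Does another planned analysis restore these subjects?**

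- The per-protocol set (9.2.4) and the observed-cases analysis (9.4.2) both lie inside the FAS.
- The ranked APOV analysis (9.4.1) and the tipping point (9.4.3) name no other set.
- The supplementary estimands in protocol 9.3.5 and SAP 5.5 change only how intercurrent events are handled.
- The ITT set (9.2.1) is defined, but no efficacy analysis is assigned to it.

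**The case against.** The best reply is that the affected group is tiny. Ability to complete the diary is an entry criterion (4.1, item 10), sites monitor transmissions and counsel subjects, and on the wording any one average up to Week 12 may be enough. Even the 5% case moves the estimate by only 0.16 SE. This stands, and it limits the weight of the point.

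A second reply is that success requires both co-primaries, so one common set is a coherent choice. That has some force, but the present set can still be reported alongside. It is also fair that a set requiring a dose conditions on a post-randomisation event too. The proposal removes the diary condition, not every such condition.

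Third, an ET scan from a very early leaver may lie close to baseline and is not a Week 24 outcome. That is true, and the illustration with scans 1-2 SD from the mean is only arithmetic. But the plan's Week 24/ET endpoint accepts such a scan.

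Four stronger inferences are not supported:

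- That no planned analysis would reveal the effect. The SAP Introduction makes the CS-3205 SAP the primary reference for methods and data handling. It is not supplied and may contain such an analysis. It may also settle how many diary days make an average, and whether a CSNS of 9 assigned after a steroid or surgery event counts as a post-baseline value.
- That everyone who leaves before Week 4 is lost. A single earlier average, such as Week 2, keeps a subject in.
- That the pooled exacerbation-frequency tests are affected in the same way. SAP 5.2 sends pooled endpoints to the ISE SAP, also not supplied.
- That SAP 5.5 already offers a way to change the CS-3205 set. It applies only the supplementary-estimand sensitivity analyses to that study post hoc.

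**Conclusion.** The inconsistency is real on the plain wording of 9.2.3, and it conflicts with the treatment policy and jump-to-control rules that the protocol itself chose for APOV. For active-arm subjects without a CT, deletion favours active treatment in expectation. For subjects with a CT, the direction is unknown. The likely size is small: 0.09-0.45 points, or 0.03-0.16 SE, if 1-5% of the active arm is affected and has no CT. That range is an assumption, since the documents give no count. The effect on time to first exacerbation cannot be sized from the documents; it is a late step in the testing sequence (step 9 in protocol 9.8.2, step 10 in SAP 5.3.2, for 372 µg). The case for acting rests on principle and low cost, not on a demonstrated material bias. It is subject to what the CS-3205 SAP says.

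**What to change.** 1. Apply the post-baseline CSNS condition to CSNS and other diary endpoints only.
2. Analyse APOV in all randomised, dosed subjects with a baseline APOV, using the observed CT, the composite score or jump-to-control as already specified.
3. Analyse time to first exacerbation in this study in all randomised, dosed subjects. State the censoring at end of follow-up, or cross-refer to the CS-3205 SAP; protocol 9.5 names only Kaplan-Meier and log-rank, and no censoring rule appears in the supplied documents.
4. Keep the current FAS as a sensitivity analysis, and report exclusions by arm and by whether a CT was available.
5. For the pooled endpoints, have the ISE SAP state one common set for both studies. This needs its own decision, because changing the set for CS-3205 is not covered by SAP 5.5.

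**Cost.** A short change to the set definition, a rerun of planned models, and no new data. The downside is a few more imputed APOV values and a slightly smaller expected difference: at 5% affected, power is about 84.0%, against 85.8-86.6% under exclusion.
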